9.6. Analysis methods – secondary outcomes

Analyses for the binary secondary outcomes will be performed as per the primary outcome for the following outcome measures

- **Surgical intervention to resolve the miscarriage (collected up to discharge from EPU care)**
- **Surgical intervention to resolve the miscarriage up to and including day 7 post-randomisation**
- **Surgical intervention to resolve the miscarriage after day 7 post-randomisation to discharge from EPU care**
- **Need for further doses of misoprostol up to day 7 post-randomisation**
- **Need for further doses of misoprostol up to discharge from EPU care**
- **Diagnosis of infection associated with miscarriage requiring outpatient antibiotic treatment (collected up to discharge from EPU care)**
- **Diagnosis of infection associated with miscarriage requiring inpatient antibiotic treatment (collected up to discharge from EPU care)**
- **Negative pregnancy test result 21 days (\pm 2 days) after randomisation**
- **Blood transfusion required (collected up to discharge from EPU care)**
- **Side effects (AEs collected up to discharge from EPU care)**
- **Death (collected up to discharge from EPU care)**
- **Any serious complications (SAEs collected up to discharge from EPU care)**

95% confidence intervals (and p-values for the key secondary outcome and safety outcomes) from the associated models will be presented according to the strategy detailed in section 5.2. No sensitivity analyses for these secondary outcome measures will be performed.

A template for reporting these binary secondary outcomes is given in Appendix D7.1 and D9.1.

Linear regression modelling will be used to compare

- **Overall patient satisfaction score (measured using the CSQ-8 questionnaire and collected upon discharge from EPU care).**
- **Duration of bleeding reported by woman (days) (collected up to discharge from EPU care)**

between the two treatment groups. The models will be adjusted for the minimisation variables as detailed in section 9.1 with the clustering effect of randomising centres accounted for by using robust standard errors at centre level. If the linear model fails to converge, centre will be dropped from the model in the first instance. If convergence of the model remains problematic, unadjusted estimates will be produced from the linear model. The adjusted mean differences between treatment groups will be presented along with the 95% confidence intervals. If residuals from the model are considered sufficiently skewed to violate the normality assumption, a Poisson regression with robust standard errors will be used. For these outcomes and for **time from randomisation to discharge from EPU care**, data will be summarized using means and standard deviations, as well as medians and inter-quartile ranges to aid the understanding of the data.

A template for reporting continuous outcomes is given in Appendix D7.2.

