4.7. Sample size

We plan to randomise 710 women, 355 participants in each group. 670 women will need to be evaluated to detect a Minimally Important Difference (MID) of 10% reduction in the rate of failure to spontaneously pass the gestational sac within 7 days (i.e. from 25% to 15%), assuming 90% power and a type I error rate of 5%. However, assuming and adjusting for a worst case

scenario of 5% attrition, the total number of participants required will be 710. The 25% [95% CI: 23% to 27%] control group estimate is taken from our systematic review (unpublished data) and the 10% MID was the most popular selection from our health professional survey (41% of those surveyed). The estimate of the control group rate will be monitored throughout the recruitment period by the independent DMC to ascertain if any deviations from this assumption will impact on the sample size calculation.

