5.2. Adjustments for multiplicity

Multiple comparisons will be allowed for by following a hierarchical testing procedure. That is to say, the null hypothesis for the primary outcome will be tested first (at the 5% significance level) and if and only if the test is statistically significant will the key secondary outcome be tested. Otherwise, no further hypothesis testing will be performed. In order to assess any signal within specific organ groups, P-values will be presented for all safety outcomes unadjusted for multiple testing, as type I error rates (false positives) are less of a concern. Results from all other secondary outcomes will be treated as exploratory rather than confirmatory. No adjustments for multiple testing will be made for confidence intervals.

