9.5. Analysis methods – primary outcome(s)

- **Failure to spontaneously pass the gestational sac within 7 days after randomisation**

The primary outcome will be summarised using number of responses with percentages. For the analysis of the primary outcome measure, a log-binomial regression model will be used to calculate the adjusted relative risk and 95% confidence intervals, after accounting for the possible clustering effect of randomising centres by using robust standard errors at centre level. The risk ratio will be adjusted for minimisation variables as detailed in section 9.1. The p-value from the associated model will be produced and used to assess statistical significance.

If the log-binomial model fails to converge, centre will be dropped from the model in the first instance. If convergence of the model remains problematic, it may be resolved by using Poisson regression with robust standard errors.¹³ In the current case, the robust standard errors will be applied at centre level to account for the clustering effect of randomising centres. If this also fails to converge, unadjusted estimates will be produced from the log-binomial model. It will be made clear in the final report why this occurred (e.g. not possible due to low event rate/lack of model convergence).

In the primary analysis, participants with missing data for any reason will be excluded. Sensitivity analyses (see Section 9.10 below) will be undertaken using the same modelling approach.

A template for reporting the primary outcome is given in Appendix D6.

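### Rare safety outcomes: with no events in one arm the planned model has no finite risk ratio, and fallbacks keyed to non-convergence usually will not catch it

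*SAP*

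**What the plan says.** SAP section 9.6 introduces its list of binary outcomes with "Analyses for the binary secondary outcomes will be performed as per the primary outcome for the following outcome measures". The list includes "Death (collected up to discharge from EPU care", blood transfusion, any SAE, any AE, and infection treated as an outpatient or as an inpatient. Section 9.5 defines the method: a log-binomial model adjusted for the minimisation variables, with robust standard errors at centre level.

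Section 5.2 adds that "P-values will be presented for all safety outcomes unadjusted for multiple testing". Section 9.6 takes those p-values from the fitted models and rules out sensitivity analyses for these outcomes. The template in Appendix D9.1 has adjusted risk ratio and p-value columns, with rows for transfusion, death and SAEs.

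The fallbacks in section 9.5 start when the model does not converge: drop centre, then use Poisson regression with robust standard errors. The last step is "If this also fails to converge, unadjusted estimates will be produced from the log-binomial model". Low event rates appear in sections 9.1 and 9.5 only as an example of why an unadjusted estimate might be reported. Section 9.8 has a frequency floor of 5%, but only for individual AE types. No rule covers an arm without events.

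**The concern.** Death and transfusion may well be absent from one arm of 355 women. A log-link model then has no finite maximum-likelihood estimate of the risk ratio: it is 0 or infinite. What the software prints depends on where the iteration stops, and it usually stops with a message of convergence. A safeguard that waits for non-convergence is therefore usually bypassed.

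The robust standard error does not show the problem. It stays small while the estimate drifts away, so their ratio gives an extreme Wald p-value. A handful of transfusions on control and none on mifepristone could be tabulated as a risk ratio near 0 with p<0.001.

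**Working it through.** **Inputs.** Section 4.7 gives the arm size: "We plan to randomise 710 women, 355 participants in each group". The SAP gives no event rates and no number of centres. Assumed here: 1, 3 or 5 events against 0, 28 centres (25 in one set of runs), and five simulated baseline covariates.

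**The plan's own figure.** For 25% against 15%, two-sided 5% and 90% power, with pooled variance under the null:

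n per arm = [1.960 × √(2 × 0.20 × 0.80) + 1.282 × √(0.25 × 0.75 + 0.15 × 0.85)]² / 0.10² = (1.109 + 0.719)² / 0.01 ≈ 334.2, so 335 per arm and 670 in all. With 5% attrition, 670 / 0.95 = 705.3, so 706, which the SAP states as 710. The sample size reproduces, and 355 per arm is a sound basis.

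**Why the fit stops.** Take 3 events on control, none on mifepristone, and the unadjusted Poisson model. The empty arm contributes minus its fitted number of events to the log-likelihood. At a log risk ratio of -18.7 this is 3 × exp(-18.7) ≈ 2.3e-8. Further movement changes the log-likelihood by less than a tolerance of 1e-7, so convergence is declared.

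**Why the robust standard error stays small.** Ignore clustering for the algebra.
- Empty arm: every residual is -μ, so its variance contribution is 355μ² / (355μ)² = 1/355, however small μ becomes.
- Control arm: the contribution is 1/3 - 1/355.
- Sum: 1/3, so the SE is √(1/3) ≈ 0.58.

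The model-based variance is about 1/(2.3e-8), an SE of about 6,600. In the simulated fits the centre-clustered SE had median 0.59, and 18.7 / 0.59 = 31.7 standard errors, p about 1e-220.

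**Simulated fits, no events on mifepristone** (40 data sets per scenario, own fitting routine, tolerance 1e-7):

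| Control vs mifepristone | Model | Converged | Robust p, median | Robust p, largest | Fisher p |
|---|---|---|---|---|---|
| 3 vs 0 | log-binomial, adjusted | 40/40 | 2.4e-205 | 4.3e-59 | 0.249 |
| 3 vs 0 | Poisson, adjusted | 40/40 | 4.4e-205 | 8.4e-65 | 0.249 |
| 3 vs 0 | log-binomial, unadjusted | 40/40 | 1.3e-220 | 1.4e-126 | 0.249 |
| 5 vs 0 | log-binomial, adjusted | 40/40 | 0 to machine precision | 9.0e-173 | 0.062 |

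Fisher's two-sided p for 3 vs 0 is 2 × (355 × 354 × 353) / (710 × 709 × 708) = 0.249. The model-based p-value for the same data was about 0.997. A separate check in statsmodels with 3 vs 0 converged in 19 to 20 of 20 data sets, with median p below 1e-240. The third row of the table is the SAP's last fallback, and it fails in the same way.

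**One event on control, none on mifepristone.** Unadjusted fits in statsmodels all converged, with median p about 1e-82 (log-binomial) or 1e-88 (Poisson), against Fisher 1.00. Adjusted Poisson converged in only 14 of 20 data sets in one set of runs and 12 of 20 in another, and a few adjusted fits gave large p-values.

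**No events on control, 3 on mifepristone.** At tolerance 1e-7 all fits converged, with median robust p of 1e-74 or smaller. At 1e-10 the robust SE rose to between 439 and 929 and median p to between 0.95 and 0.98. In statsmodels, with 3 or 5 events, p was undefined in 6 to 13 of 20 data sets per scenario, and medians were otherwise mostly 0.1 to 0.4.

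**Events in both arms.** No comparable failure: 3 vs 1 gave robust p 0.32 to 0.35 (Fisher 0.62), and 10 vs 5 gave 0.19 to 0.21 (Fisher 0.30).

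**How often.** With a common event rate r and q = (1 - r)^355, the chance that exactly one arm is empty is 2q(1 - q). For assumed rates of 0.1%, 0.25%, 0.5% and 1% this is 42%, 48%, 28% and 5.5%. At 0.01% both arms are empty with probability 93%.

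**The case against.** The SAP leaves some room. Section 9 applies adjusted models where possible, section 9.1 offers non-convergence as an example of why adjustment might fail, and both 9.1 and 9.5 recognise low event rates. Section 9.8 already restricts rarer AE types to description. Section 5.2 treats safety p-values as a screen in which false positives matter less. Appendix D9.1 prints counts beside the ratio, so a qualified statistician would probably notice, and Appendix A allows documented deviations.

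This lowers the severity but does not close the gap. None of these passages names a method that works with an empty arm. Under section 5.6 the remedy would normally be chosen after database lock, with allocation known.

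Several stronger readings are tempting and are not supported:
- **That the fallbacks can never start.** Some adjusted fits with a single event did fail to converge. If the centre-level robust SE is then dropped, p is about 1 with a uselessly wide interval, which is no better.
- **That the plan would reliably produce a false alarm against mifepristone.** That needs an empty control arm, where the p-value swings with tolerance and software.
- **That every listed outcome gets a false p-value.** The infection outcomes receive only a confidence interval, which is equally invalid with an empty arm. If both arms are empty there is no comparison to misreport. Nothing in the SAP suggests that any SAE would be absent from an arm.
- **That all small counts break the model.** The runs with events in both arms do not show this.

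**Conclusion.** The point stands as a gap in the rule for a zero cell. With no events on mifepristone, the planned analysis typically reports convergence and an absurdly small p-value (3 vs 0: below 1e-100 in most runs, Fisher 0.25), which is a false claim of benefit. With no events on control, the result is unstable or undefined. In neither case does any step of the fallback sequence give a valid estimate.

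The mechanism follows from the algebra. The exact p-values rest on assumed event counts, centre numbers and covariates, and on Python fits; the SAP names Stata and SAS, which were not run. How often an arm would be empty depends wholly on event rates that the SAP does not give.

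Severity: should-fix. The primary and key secondary conclusions are not affected.

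**What to change.** Add to sections 9.6 and 9.8, with a matching footnote in Appendix D9.1:
- If either arm has no events for a binary outcome, no regression model is fitted. Report n (%) by arm, an exact or score 95% confidence interval for the risk difference and, for safety outcomes only, Fisher's exact p-value.
- If neither arm has an event, report counts only.

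Trigger the rule on the zero cell, not on convergence. A wider minimum-event threshold is optional; the runs do not show that one is needed.

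Name the interval method in advance. For 3/355 vs 0/355 the Newcombe interval for the risk difference of 0.85% is -0.36% to 2.45%, in line with Fisher. For 5/355 vs 0/355 it is 0.07% to 3.25% and excludes zero, while Fisher gives 0.062, so the SAP should say how such a disagreement is read.

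The cost is a few sentences. The comparisons concerned would be unadjusted, slightly conservative, and expressed as risk differences instead of risk ratios.

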9.7. Analysis methods – exploratory outcomes and analyses

Any data that does not form a pre-specified outcome will be presented using simple summary statistics by treatment group (i.e. numbers and percentages for binary data and means (or medians) and standard deviations (or inter-quartile ranges) for continuous normal (or non-normal) data.

9.8. Safety data

Information for adverse events was captured in AE forms and categorised by CTCAE category¹² (v4.0). Only AEs graded 3, 4 or 5 were required to be reported for the MifeMiso trial.

Information for serious adverse events was captured in SAE forms and categorised by CTCAE category¹² (v4.0).

AEs (side effects) that occur with a frequency of >5% in at least one of the treatment groups will be summarised by treatment group using frequencies and percentages, and analysed as for all secondary binary outcomes, as detailed in section 9.6. All other AEs will be categorised as 'other' side effects and summarised only. See Appendix 9.1 for the template for reporting AEs.

The number and percentage of women experiencing any adverse event (AE, listed as side effects in secondary outcomes), any serious adverse event (SAE, listed as serious complications in secondary outcomes) and suspected unexpected serious adverse reaction (SUSAR) will be

presented by treatment group. The total number of AEs, SAEs and SUSARs in each treatment group will also be given, along with a descriptive table of the events including CTCAE category for reporting, date of onset, date resolved, severity, relatedness and the causality assessment by the site PI (or delegated clinician) and details of the event.

A template for reporting is given in Appendices D9.2, 9.3 and 9.4.

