- a) Was the woman diagnosed with an infection that was associated with miscarriage?
- b) Were they treated as an inpatient?
- c) Was the woman prescribed antibiotics for the infection?

A binary outcome will be defined based on whether or not the above three conditions were satisfied simultaneously. If any are missing then the outcome will be coded as MISSING.

- **Negative pregnancy test result 21 days (\pm 2 days) after randomisation**

Reported on Section D (pregnancy test result) on the Outcomes form by answering YES to the question "Did the woman provide a pregnancy test result?" with a negative test result. A binary outcome will be defined based on whether the test result is positive or negative and a missing value will be taken if either the woman did not provide a pregnancy test result or the result is missing.

- **Time from randomisation to discharge from EPU care (described using summary statistics only)**

Reported on Section F (clinical outcomes until discharge) on the Outcomes form by answering the question "Date of final discharge from EPU care following a negative pregnancy test", and by calculating:

Date of final discharge from EPU care following a negative pregnancy test - Date of randomisation.

- **Blood transfusion required (collected up to discharge from EPU care)**

Reported on Section F (clinical outcomes until discharge) on the Outcomes form by answering the question "Did the woman require a blood transfusion from randomisation up until discharge from EPU care?" A binary variable will be defined. If a woman withdrew or was lost to follow up before being discharged, the binary outcome will take missing values.

- **Side effects (collected up to discharge from EPU care)**

Reported on the AE form AEs that are specified with a severity grade of 3, 4, or 5, from the first administration of trial treatment until discharge from EPU care. Events will be reported based on CTCAE category¹².

A binary outcome will be derived if a woman has at least one AE.

- **Death (collected up to discharge from EPU care)**

Reported on the SAE form.

- **Any serious complications (collected up to discharge from EPU care)**

Reported on the SAE form from the first administration of trial treatment until discharge from EPU care.

A binary outcome will be derived if a woman has at least one SAE.

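### Section 5.2 promises p-values to detect organ-group safety signals, but the >5% rule in 9.8, applied to grade 3–5 events only, leaves categories below 18 of 355 women without a between-arm comparison

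*SAP*

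**What the plan says.** Section 5.2 gives the reason for testing safety outcomes: "In order to assess any signal within specific organ groups, P-values will be presented for all safety outcomes". The p-values are unadjusted, "as type I error rates (false positives) are less of a concern".

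Section 9.8 limits what is collected: "Only AEs graded 3, 4 or 5 were required to be reported for the MifeMiso trial". It then sets the rule for individual side effects. Those meeting the condition "AEs (side effects) that occur with a frequency of >5% in at least one of the treatment groups" are summarised and analysed like the binary secondary outcomes of 9.6. For the remainder, "All other AEs will be categorised as 'other' side effects and summarised only".

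Section 9.4 defines the side-effects outcome in two ways that bear on this. It names a reporting unit, "Events will be reported based on CTCAE category", and a pooled indicator, "A binary outcome will be derived if a woman has at least one AE".

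The denominators come from 4.7: "We plan to randomise 710 women, 355 participants in each group".

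Appendix D9.1 has rows for transfusion, any side effect, up to ten named side effects, other side effects, death and any SAE, under a risk-ratio and a p-value column. D9.2 gives totals. D9.3 and D9.4 list individual events under each arm with their CTCAE category.

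**The concern.** Section 5.2 favours sensitivity: accept false positives so that a signal in one organ group is not missed. The threshold in 9.8 works the other way. A 5% cut may be reasonable where all grades are collected and common mild events fill the table. Here mild and moderate events are not collected, so the cut falls on severe events alone.

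If most categories of severe event fall below 5% in both arms, the only tests left are of pooled or single outcomes, and none of those is specific to an organ group. An excess of severe events in one category could then reach the report as lines in a listing, with no count of women by arm, no estimate and no interval.

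**Working it through.** **Inputs.** 355 women per arm (SAP 4.7); threshold above 5% in at least one arm (9.8); grades 3–5 only (9.8); two-tailed p-values (5.1). The SAP states no expected grade 3–5 rates, so all event rates below are assumptions.

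**The denominator.** 25% v 15%, two-sided 5%, 90% power and no continuity correction give 335 per arm, or 670, which matches 4.7. Allowing 5% attrition, 670 / 0.95 = 705.3, so 706; the plan's 710 is consistent with that. 710 / 2 = 355 per arm.

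**The threshold as a count.** 0.05 × 355 = 17.75, so the smallest qualifying count is 18 (18/355 = 5.07%) and the largest that does not qualify is 17 (4.79%). With 335 per arm, 0.05 × 335 = 16.75, so the smallest qualifying count is 17.

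**What falls below it.** Two-sided Fisher exact tests, 355 per arm:

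| Women with the event | Percent | p |
|---|---|---|
| 17 v 0 | 4.8 v 0 | 0.000013 |
| 17 v 5 | 4.8 v 1.4 | 0.015 |
| 12 v 2 | 3.4 v 0.6 | 0.012 |
| 10 v 1 | 2.8 v 0.3 | 0.011 |
| 6 v 0 | 1.7 v 0 | 0.031 |

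None would be compared under 9.8. Against zero events in the other arm, six women already give p < 0.05, while the rule asks for 18.

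**How often a category qualifies.** For true rates a and b, the probability that at least one arm has 18 or more women is 1 − P(X ≤ 17 | 355, a) × P(X ≤ 17 | 355, b). The last column is the share of Fisher-significant (p < 0.05) results in which neither arm passes the cut.

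| Assumed rates | Either arm passes 5% | Fisher p < 0.05 | Share of those not compared |
|---|---|---|---|
| 2% v 1% | 0.04% | 11% | 99.7% |
| 3% v 1% | 2.3% | 38% | 94% |
| 4% v 1% | 18% | 68% | about 74% |
| 5% v 1% | 51% | 87.5% | 42% |

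At 335 per arm the chances of passing for the last three rows are similar: 2.6%, 19.0% and 51.0%.

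**Whether the pooled test covers the gap.** Suppose a category shows 10 v 1, and b other women in each arm have some other grade 3–5 event, with no overlap. The any-AE comparison is then (10 + b) v (1 + b) of 355. For b = 5 it is 15 v 6, p = 0.07; for b = 10, 20 v 11, p = 0.14; for b = 50, 60 v 51, p = 0.41. A larger excess survives longer: with 17 v 0 the pooled p is 0.001, 0.006 and 0.022 at b = 5, 10 and 18, then 0.053 at b = 30 and 0.11 at b = 50.

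**Consistency of the text.** Section 9.8 does not say whether the 5% applies to a single AE term or to a CTCAE category; the gap is wider for single terms. D9.1 puts the other-side-effects row under risk-ratio and p-value columns, although 9.8 says those events are not analysed.

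**The case against.** A reader might infer that only side effects above 5% are analysed, or that smaller imbalances are hidden. The SAP does not support either reading. Section 4.4 defines four safety outcomes: transfusion, side effects, death and serious complications. Sections 9.4 and 9.6 and Appendix D9.1 give each a between-arm analysis with a p-value at any frequency. Read literally, the promise in 5.2 of p-values for all safety outcomes is met, and the 5% rule governs only the breakdown beneath the pooled side-effects outcome. D9.3 and D9.4 set out every event by arm with its CTCAE category, so 17 v 0 would be visible to a careful reader. Section 9.7 asks for numbers and percentages by group for data outside the pre-specified outcomes, and might be read to require category counts.

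A cut also has a practical reason. The analysis is an adjusted log-binomial model, and 9.1 and 9.5 foresee failure with low event rates. The illustrative p-values are chosen by example and unadjusted over an unstated number of categories, so a value near 0.01 would not be strong evidence of harm.

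Most of this stands, and it limits the point to the organ-group comparison. It does not remove it. If only the pooled outcomes were meant, the reference in 5.2 to specific organ groups would have nothing to apply to except rows above 5%. Listings give no count of women per category, no percentage and no interval. Section 9.7 would at most give counts, and whether it reaches side effects, themselves a pre-specified outcome, is unclear. Sparse data call for another method rather than no comparison; the SAP already plans to model death and transfusion, with an unadjusted fallback.

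**Conclusion.** The point holds as a mismatch between the purpose stated in 5.2 and the rule in 9.8. At 355 per arm, a side effect seen in 17 or fewer women in each arm gets no comparison of its own, although 6 v 0 would already be nominally significant, and no template counts women by category and arm. The pooled tests only partly compensate: under the assumed backgrounds of 5 to 50 other affected women per arm, a 10 v 1 excess gives a pooled p between 0.07 and 0.41.

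The threshold count follows from the SAP alone. How many categories fall below it depends on grade 3–5 rates that the SAP does not give; a category above 5% would be compared as 5.2 intends. The primary and key secondary inferences are unaffected. This should be changed because the stated safety aim is otherwise not delivered.

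**What to change.** In 9.8 and D9.1, replace the >5% rule for grade 3–5 adverse events with a table of women having at least one event in each CTCAE category, by arm, with an effect estimate, 95% CI and unadjusted p-value. Use the 9.6 log-binomial model where it can be fitted and an exact method where events are too sparse; the exact method is a suggestion here and is not named in 5.2. State that any remaining frequency cut applies to individual terms, not to categories. Align the other-side-effects row of D9.1 with 9.8 by leaving its risk-ratio and p-value cells blank.

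The events are already collected and categorised, so no new data are needed. The cost is more table rows and more unadjusted p-values, some of which will be small by chance. Section 5.2 already accepts that.
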